There are very few interventions to improve the success of ECV. A randomized trial of nulliparous patients undergoing ECV with and without spinal anesthesia found a success rate of 32% without and 67% with anesthesia. While this is an impressive improvement in success, many of our patients do not wish to have regional anesthesia. Regional anesthesia also increases the length of stay and cost of the ECV procedure. One potential method of improving ECV success is to elevate the fetal buttocks during the procedure, although this has been poorly studied. One group reported that they had zero successful ECV procedures when the buttocks were lower than -1 station, versus a 66% success if the buttocks were at or higher than -3 station.

The Safe Obstetric Systems Inc. Fetal Pillow is a balloon device approved by the United States Food and Drug Administration (FDA) for elevating the fetal head during cesarean deliveries performed during the 2nd stage, after the patient has been pushing. The device is placed into the vagina, filled with sterile saline, and inflated to push the head up and out of the pelvis. Using the device to elevate the fetal buttocks prior to an ECV is an off-label usage of the product. Although unlikely, it is possible that the Fetal Pillow may decrease ECV success rates or cause unforeseen harm to the mother or fetus.

The objective of this research project is to assess the efficacy of the Fetal Pillow during ECV procedures for nulliparous women without regional anesthesia.

Study Objectives

Primary Objective

The primary objective of this study is to evaluate the successful conversion of a breech to vertex presentation. Successful conversion will be confirmed via ultrasound immediately following the ECV procedure.

Secondary Outcomes

Maternal outcomes:

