3. EGA
4. Name of obstetrician performing ECV procedure
5. Presence of inflated Fetal Pillow
6. Presence of terbutaline
7. Presence of palpable fetal head
8. Estimated fetal weight (kg)
9. Fetal head position *confirmed by ultrasound
10. Fetal back position
11. Position of fetal neck
12. Location of placenta
13. Amniotic fluid index (4 quadrant total)
14. Fetal station (-3 through +3)
15. Maternal cervical dilation (cm)
16. Presence of rupture of membranes within 1 hour of procedure
17. Presence of 3 or more contractions in 10 minutes immediately prior to procedure
18. Bleeding equal to a menstrual period during or within 1 hour of the ECV procedure.
19. Development of a pelvic hematoma during or within 1 hour after the ECV procedure.
20. Development of a vaginal laceration during insertion of the device, the ECV procedure, or removal of the device.
21. Presence of fetal bradycardia
22. Presence of fetal heart rate decelerations
23. Presence of delivery within 1 hour of procedure
24. VAS pain score immediately prior to ECV (-3 minutes)
25. VAS pain score immediately after insertion of Fetal Pillow (+ 2 minutes)
26. VAS pain score after inflation/sham inflation (+ 1 minute)
27. VAS pain score immediately after each ECV procedure attempt, maximum of 4 attempts (+ 2 minutes)
28. Total number of attempts
29. Procedure successful Y N (Primary Outcome) *confirmed by ultrasound
30. Fetal head position post ECV *confirmed by ultrasound
31. Number of forward rolls
32. Number of reverse rolls
33. Note which procedure was successful

34. Did patient request to have spinal or epidural anesthesia after initiation of ECV procedure (off of study protocol): Y N
35. Presence of regional anesthesia prior to ECV procedure (Excluded from study)
36. Length of time from start of procedure to hospital discharge
37. Cost of hospital stay for ECV procedure

Study Design

Research Design

This is a prospective, randomized double-blind clinical trial evaluating the effect of a balloon device to elevate the fetal buttocks during external cephalic version procedures. Eligible study population: pregnant women between 37-40 weeks estimated gestational age with a breech presenting baby and no contraindications to ECV.

Study Agent, Device, and/or Intervention Description:

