Visit 1 (ECV Procedure): The PI/Sub-I will meet the patient at the labor and delivery area, and review both the ECV procedure and possible study inclusion. The patient and researcher will sign consent forms if the patient qualifies for study inclusion and agrees to participate.

After weighing the patient, calculating a body mass index, performing a digital cervical exam, and performing a fetal non-stress test and obstetric ultrasound, all routine components of the ECV process, the PI/Sub-I will verify there are no exclusion criteria. Assuming that an ECV is still necessary and safe, the patient will receive a 0.25mg subcutaneous injection of terbutaline, a medication to quiet the uterus that is commonly used for ECV procedures. The midwife/physician performing the device inflation or sham inflation will open the randomization envelope. The researchers are blinded to patient randomization. All patients will mark a line on a 100mm VAS to assess pre-procedure pain.

The researcher will show the patient the device, open the sterile container, and insert the device into the vagina per manufacturer's guidelines for all patients in the study. All patients will mark a line on a 100mm VAS to assess post-insertion pain. The study physician will then obtain the assistance of a trained midwife/physician to inflate the device or perform a sham inflation. For the physician to remain blinded, the physician will leave the room during the time of the inflation/sham inflation. This will be documented in the source documents. Midwives/Physicians performing the inflation or sham inflation will have undergone previous training. Inflating the

Fetal Pillow is similar, although less difficult, than other balloon devices commonly used on the labor and delivery unit. The assisting midwife/physician will inflate the device with 180 mL of saline for those patients randomized to inflation. This will occur under a sheet so that the patient is blinded to the randomization scheme. If the patient is randomized to no inflation, the midwife/physician will perform a sham inflation, also under a sheet. All patients will mark a line on a 100mm VAS to assess post-inflation/sham inflation pain. The assisting midwife/physician then leaves the room, and the study physician reenters the room and proceeds with the ECV procedure.

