Regardless of randomization, at this point the ECV procedure proceeds using normal routine. Once completed, all patients will mark a line on a 100mm VAS to assess post-ECV pain. The ECV will be attempted up to four times and VAS will be assessed after each attempt.

The research physician will then remove the Fetal Pillow and perform a post procedural ultrasound to verify fetal position. Regardless of randomization, the procedure is completed per the usual routine of fetal monitoring, assessing for labor or bleeding, discussing post-procedure care, then discharge home (or, less likely, admitting for either observation or delivery).

The researcher will fill out the ECV portion of the data collection form.

Visit 2 (Labor and Delivery): There are no study interventions during this visit. The file linking the subject's FIN and study numbers will be sent to the honest broker who will then extract the data for delivery outcomes for the mother and neonate along with the final cost calculations. This data will be entered into a spreadsheet by the honest broker and then sent back to the research team. The research team will send the file linking the subject's FIN and study numbers at the intervals outlined in the safety monitoring plan (first 10 randomized subjects and every 20 subjects thereafter). The investigators are unblinded to patient randomization after the ECV procedure has been completed and during data collection for delivery and neonatal outcomes.

Data collection for patients delivering outside of AdventHealth facility. Patients will sign a release of records; study coordinator will request records from delivering facility and delivery outcomes data will be imported into spreadsheet linked to FIN.

Study Duration:

Estimated date of study completion: March 31, 2023

- Projected start date: November 1, 2020.
- Projected completion of enrollment of all study subjects: November 1, 2022.
- Projected final data collection date: March 1, 2023.

Materials of Human Origin: N/A

Study Outcome Measures (Endpoints)

Primary Outcome:

Proportion of patients undergoing ECV who have a successful outcome with and without an inflated Fetal Pillow.

Secondary Outcomes:

As noted, many of these data points are normally recorded in the medical record during an ECV procedure and subsequent delivery, regardless of study participation.

Subject Information (maternal):

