Clinical trial monitoring is conducted to ensure that the rights and well-being of trial participants are protected. Reported trial data are accurate, complete and verifiable.

Clinical trial monitoring will be conducted by AdventHealth Office of Research Integrity monitoring team to ensure compliance with all applicable federal and state regulations, ICH GCP E6 (R2) standards and approved protocol. This study will be monitored using a risk-based approach. A monitoring plan will be created to ensure patient safety, data quality and integrity is ongoing throughout the life of the study. The frequency and elements of monitoring will be outlined in the monitoring plan. The monitor will ensure study is conducted, recorded and reported as required by federal regulations and IRB of record. Monitoring will be conducted on-site and/or remote. After completion of site monitoring, a report will be provided to PI and study team. The PI and study team are required to review the report and work on significant findings or discrepancies to resolution. If any findings are required to be reported to the IRB, the PI will be made aware and prompted to self-report. All serious and continuing non-compliance is shared with the Research Oversight Committee who may require appropriate actions.

Protocol Deviations

All deviations and SAEs must be reported promptly to AH ORI and regulatory team. SAEs must be reported within 24 hours of discovery. Any SAE required to be reported to the FDA and IRB will be completed with the assistance of the central regulatory team in conjunction with the principal investigator and study team.”

Data Sharing (outside of AdventHealth Orlando): N/A

Sample Size Determination

Based on prior studies of patients without regional anesthesia who had a success rate of approximately 49%, and assuming a 1:1 allocation of intervention and control subjects, with an 80% power, and a 2-sided 5% significance level, we calculated a sample of size of 69 in each group to increase the success rate from 49% to 73.5%. Assuming a 10% case dropout rate we will enroll 76 patients in each arm (152 total participants).

Statistical Analysis Plan

Primary Objective Analysis

The success of ECV procedures for the intervention group compared to the control group will be analyzed using chi-square and Fisher exact tests. A P value of <0.05 will be considered statistically significant.

Secondary Objective Analysis

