Maternal and neonatal outcomes will be analyzed using chi-square and Fisher exact tests for categorical variables, unpaired t-tests for continuous variable, and non-parametric tests for continuous variables that are not normally distributed. P values <0.05 will be considered statistically significant.

Potential Risks and Benefits

Potential Benefits

The Fetal Pillow device may improve the ECV success rate.

Potential Risks

Although unlikely based on prior device usage during 2nd stage arrest, it is possible the device may cause vaginal bleeding, increased pain during the procedure, or either no change in success or a lower success rate compared to performing the procedure without the device. Terbutaline administration may cause maternal tachycardia, irritability, chest pressure or chest pain. While loss of confidentiality is a potential risk to patients, patient information will be de-identified prior to analysis and only study personnel will have access to patient information. The United States Food and Drug Administration has determined that this study protocol is a nonsignificant risk (NSR) study (Review # Q191927, notification received December 18, 2019).

Mitigation of Risks

Patients will be asked prior to administration of terbutaline if they have contraindications, which is standard practice prior to using this medication.

Provisions to Protect the Privacy Interest of Subjects

The steps to protect the privacy of subjects have been described previously. Briefly, study documentation and patient information will be stored in a separate file on a password-protected laptop stored in a locked office. Drs. [name], [name] and research team will have access to both files.

Early Withdrawal of Subjects

Investigator Withdrawal of Subjects.

Inability to place Fetal Pillow: If the Fetal Pillow cannot be placed, for example due to pain, or the Fetal Pillow cannot be inflated, the patient will be withdrawn from the study. However, she may undergo an attempted ECV outside of the study protocol if she wishes.

Delivery at a hospital outside of the AdventHealth Orlando system: If the patient delivers outside of the AdventHealth Orlando system she will be withdrawn from the study analysis.

Subject Request for Withdrawal from Study

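### No primary analysis set is defined, and the withdrawal rules act after randomisation: outside deliveries leave the analysis with their result already known, and failed inflation can withdraw women from one arm only

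*Combined protocol and SAP*

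**What the plan says.** **Primary analysis.** In the section Primary Objective Analysis the plan states: "The success of ECV procedures for the intervention group compared to the control group will be analyzed using chi-square and Fisher exact tests". No intention-to-treat, per-protocol or other set is named there or elsewhere. Study Outcome Measures words the endpoint as "Proportion of patients undergoing ECV who have a successful outcome with and without an inflated Fetal Pillow".

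**Timing of the endpoint.** Under Primary Objective: "Successful conversion will be confirmed via ultrasound immediately following the ECV procedure". The primary result is therefore known at Visit 1, before delivery.

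**Failed placement or inflation.** Early Withdrawal of Subjects covers a device that cannot be placed, "or the Fetal Pillow cannot be inflated, the patient will be withdrawn from the study". It adds: "However, she may undergo an attempted ECV outside of the study protocol if she wishes".

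**Outside delivery.** The same section says: "If the patient delivers outside of the AdventHealth Orlando system she will be withdrawn from the study analysis". Visit 2, by contrast, has women sign a records release so that the outside facility's delivery data can be requested and imported. It also says that investigators are unblinded once the ECV is complete.

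**Order of events at Visit 1.** The person who inflates or sham-inflates opens the randomisation envelope, and this is described before insertion. The device is inserted in both arms by a blinded physician. Only the inflation arm has it filled.

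**Already covered.** The percentage of withdrawals and the reasons will be reported, though not by arm. Sample Size Determination adds 10% for dropout.

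**The concern.** The primary test compares two groups whose membership is not fixed in advance, and two rules can change that membership after randomisation.

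1. *Outside delivery.* The rule removes women from the analysis without limiting this to delivery outcomes. Read literally, it discards an observed primary result because of something that happens later. It also conflicts with Visit 2, which collects these women's delivery data. Investigators know arm and ECV result by then, so a choice left open would be made with both in view.

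2. *Failed inflation.* This can occur only in the inflation arm. If the women concerned leave the primary comparison, the inflation arm is selected and the control arm is not. The device looks better if they are harder to turn than average, is unaffected if they are average, and looks worse if they are easier to turn. Follow-up for Withdrawn Subjects asks only women who choose to withdraw, and only about delivery data. The off-protocol ECV result would then be missing, and the direction of any bias could not be checked afterwards.

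Failed placement is a lesser matter: insertion is the same in both arms and done blinded, so losses should be balanced.

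**Working it through.** **The plan's own figure.** Inputs from Sample Size Determination: 49% vs 73.5%, two-sided 5%, 80% power, 1:1. The pooled normal formula gives 60.9 per arm. With the continuity correction, n' = (n/4)[1 + √(1 + 4/(n·0.245))]² = 68.8, so 69, as stated. Then 69 × 1.10 = 75.9, so 76 per arm. Loss covered by that allowance: 1 − 69/76 = 9.2%.

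**Failed inflation, no true effect.** From the plan: 49% success and 76 per arm. Assumed, because the documents give no rates: a share f of the inflation arm cannot be inflated, and those women would succeed at rate s. If they are removed, the retained rate is (0.49 − f·s)/(1 − f), and the bias is that rate minus 0.49.

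- f = 2%, s = 0: 0.49/0.98 = 50.0%, bias +1.0 point
- f = 2%, s = 25%: 0.485/0.98 = 49.5%, bias +0.5
- f = 5%, s = 0: 0.49/0.95 = 51.6%, bias +2.6
- f = 5%, s = 25%: 0.4775/0.95 = 50.3%, bias +1.3
- any f, s = 49%: bias 0
- f = 5%, s = 73.5%: 0.45325/0.95 = 47.7%, bias −1.3

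False-positive rates come from exact enumeration of all 2×2 tables at P<0.05, with the number un-inflatable distributed Binomial(76, f) in the inflation arm only:

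| f | s | chi-square (uncorrected) | Fisher |
|---|---|---|---|
| 2% | 0 / 25 / 49% | 5.06 / 4.93 / 4.89% | 4.05 / 3.94 / 3.91% |
| 5% | 0 / 25 / 49% | 6.16 / 5.29 / 5.02% | 5.49 / 4.70 / 4.45% |

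The s = 49% entries are the no-bias reference. Against them, the excess is at most 0.2 points at 2% and about 0.3-1.1 points at 5%. On 76 women, 2% is about 1.5 women and 5% about 3.8.

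**Outside delivery.** Loss unrelated to outcome causes no bias, and up to about 9% leaves the planned 69 per arm. If loss depends on the ECV result, the retained success rate is p(1−a)/[p(1−a) + (1−p)(1−b)], where a and b are the loss rates among successes and failures (assumed).

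- a = 5%, b = 15%: 75.6% − 51.8% = 23.8 points, against the planned 24.5
- a = 15%, b = 5%: 71.3% − 46.2% = 25.1 points

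**Power if all women are kept as randomised.** The inflation-arm rate is (1 − f)·0.735 + f·s. Exact Fisher power at 76 per arm is 85.2% with no failures.

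- f = 2%, s = 0 to 49%: rate 72.0-73.0%, power 80.0-83.6%
- f = 5%, s = 0 to 49%: rate 69.8-72.3%, power 70.6-81.0%

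**The case against.** The strongest reply is that being withdrawn from the study is not the same as being dropped from the analysis. Only the outside-delivery rule mentions the analysis. That is correct: for failed inflation, exclusion is an inference. But no text keeps these women in or arranges to record their ECV result, so the ambiguity remains a gap.

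A second reply is that the outside-delivery rule was meant for delivery outcomes only. It may have been, but the section does not say so, and Visit 2 contradicts it even for delivery outcomes.

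A third is that failed inflation is probably uncommon. Visit 1 says that inflating the "Fetal Pillow is similar, although less difficult, than other balloon devices commonly used on the labor and delivery unit". That is not a rate, but it points to small numbers. The 10% dropout allowance also absorbs moderate random loss. Both points stand and limit the size of the concern.

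Two stronger readings are tempting, and the documents support neither. A reader might infer from the endpoint wording, and from the data item "Presence of inflated Fetal Pillow", that women will be grouped as treated, with un-inflated women counted as controls. The analysis section compares intervention with control, and the endpoint wording is naturally shorthand for those arms. The withdrawal rule takes un-inflated women out, and their later ECV result is not recorded, so they could not be counted with controls. A reader might also infer a large bias in favour of the device. At the rates examined it is small, and it vanishes or reverses if the removed women are average or easier to turn.

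**Conclusion.** The concern holds. The primary analysis set is undefined. One rule, as written, discards known primary results and contradicts Visit 2. Another can withdraw randomised women from one arm only, with no record of their outcome. This needs correction because it leaves the primary comparison open, not because a large distortion is expected. With 49% success, 76 per arm and removed women succeeding at 0-25%, the bias is 0.5-1.0 points at 2% failed inflation and 1.3-2.6 points at 5%, with chi-square false positives of 4.9-5.1% and 5.3-6.2%. Outside-delivery loss mainly costs sample size. The failure shares, the success rates of removed women and the loss rates are all assumptions. The structural findings do not depend on them.

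**What to change.** 1. State that the primary analysis compares women by assigned arm and includes every randomised woman with a post-ECV ultrasound result, whether or not the device was placed or inflated and wherever she delivers.
2. Reconcile Visit 2 with Early Withdrawal of Subjects, and use the released outside records for delivery outcomes.
3. With the woman's agreement, record the ultrasound result of any off-protocol ECV and whether regional anesthesia was used.
4. Report failed placement and failed inflation by arm.
5. Pre-specify three sensitivity analyses: women with no ECV result counted as failures; off-protocol ECVs under regional anesthesia excluded; device-deployed women only. The first is needed because the set in item 1 still omits women without a result.

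The cost is protocol and SAP wording, one consent item and one data field. Keeping un-inflated women also dilutes the effect: as-randomised Fisher power falls from 85.2% to 80.0-83.6% at 2% failed inflation, and to 70.6-81.0% at 5%. Keeping outside deliveries costs no primary data.

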Patient requests withdrawal: Patients who request withdrawal for any reason will be immediately withdrawn. If a patient initially consents to have the Fetal Pillow placed, then changes her mind before or during the procedure, the researcher will remove the device and offer the patient the opportunity to proceed with an ECV attempt off-protocol. Researchers will ask the patient if they can complete data collection for delivery and proceed according to the patient's wishes. There are no known or suspected harms from withdrawing from the study.

Data Collection and Follow-up for Withdrawn Subjects

Patients electing to withdraw from the study will be asked if they consent to data collection for delivery. If they decline this, then data collection will discontinue, and the data collection sheet will be stored as deidentified data in case the patient's reason for withdrawal (for example, excessive pain) is identified as a side effect of the device. The percentage of patients withdrawing and the reasons for withdrawal will be calculated and included in any manuscript submissions.

Adverse Event Reporting

Adverse events will be collected from the time of insertion up to 1 hour after the ECV procedure and followed until discharge. Adverse events such as excessive pain or bleeding will be recorded as part of the data collection. Adverse events of special interest will be reported according to AdventHealth Orlando IRB policies

Adverse events of special interest include:

Term	Mild	Moderate	Severe	Serious	Serious
------	------	----------	--------	---------	---------

Vaginal Hemorrhage	Mild symptoms; intervention not indicated	Moderate symptoms; intervention indicated	Transfusion indicated; invasive intervention indicated; hospitalization	Life-threatening consequences; urgent intervention indicated	Death
Pelvic Hematoma	Mild symptoms; intervention not indicated	Minimally invasive evacuation or aspiration indicated	Transfusion; invasive intervention indicated	Life-threatening consequences; urgent intervention indicated	Death
Vaginal Laceration	Separation of the perineal skin only	Injury to the perineal muscles but not the sphincter or rectum	Injury to the perineal muscles and anal sphincter	Injury to the perineal muscles, sphincter, and rectal mucosa	Death

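### A woman who withdraws before or part-way through the ECV has no stated primary outcome or analysis arm; leaving her out would overstate success and could favour the inflated device

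*Combined protocol and SAP*

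**What the plan says.** Under Subject Request for Withdrawal from Study the rule is "Patients who request withdrawal for any reason will be immediately withdrawn". If a woman agreed to the device and then changes her mind, whether beforehand or while the procedure is under way, "the researcher will remove the device and offer the patient the opportunity to proceed with an ECV attempt off-protocol". Under Data Collection and Follow-up for Withdrawn Subjects, the provision for later data is this: "Patients electing to withdraw from the study will be asked if they consent to data collection for delivery". A woman who refuses has nothing more collected, and her sheet is kept in de-identified form in case her reason for leaving proves to be a side effect. That section also promises that "The percentage of patients withdrawing and the reasons for withdrawal will be calculated and included in any manuscript submissions".

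The primary outcome (Procedural Outcomes, item 29) is success yes or no, confirmed by ultrasound. Visit 1 states "The ECV will be attempted up to four times and VAS will be assessed after each attempt", then device removal, then the ultrasound. Study Outcome Measures defines the primary outcome as a proportion of women who undergo ECV, not of all randomised. The Statistical Analysis Plan names chi-square and Fisher tests for it. It gives no analysis set, no intention-to-treat statement and no rule for a missing primary outcome. Sample Size Determination adds "Assuming a 10% case dropout rate we will enroll 76 patients in each arm (152 total participants").

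**The concern.** The primary outcome is available within the randomisation visit, so almost no woman needs to be without one. Yet the rule takes a woman out at the point where the outcome is about to be read, and the only data it asks for afterwards concern delivery. Her presentation at the moment she stops, and the result of any off-protocol ECV, are not mentioned. If presentation is not recorded then, it may not be recoverable.

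A woman who withdraws before or between attempts has, at that moment, a fetus that has not been turned. If such women drop out of the denominator, no converted woman drops out with them at that point, so the remaining success rate rises. The rise differs by arm if stopping does. Potential Risks names more pain as a possible effect of the device, the withdrawal section gives excessive pain as its example reason, and only one arm has the balloon filled during the attempts. Tolerability could then enter the efficacy comparison.

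Visit 2 states that investigators are unblinded once the ECV is over. An unwritten rule on whom to count would therefore be settled by people who know the arm.

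**Working it through.** **The plan's own figure.** Inputs from Sample Size Determination: 49% v 73.5%, 80% power, two-sided 5%, 1:1 allocation. The two-proportion formula with continuity correction gives 69 per arm, as stated (61 without the correction). The enrolment figure is 69 × 1.10 = 75.9, rounded to 76 per arm, 152 in total. So the plan expects about 7 women per arm (76 − 69) to be unavailable for analysis.

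**Effect on the observed rate.** Let p be the true success rate in an arm with every randomised woman counted, w the share withdrawn and left out, and s the share of those who would have counted as successes.

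Observed rate = (p − w·s) / (1 − w)

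With p = 0.49 and s = 0 (all withdrawn women counted as not converted):
- w = 2%: 0.49 / 0.98 = 50.0%
- w = 5%: 0.49 / 0.95 = 51.6%
- w = 10%: 0.49 / 0.90 = 54.4%, which is 5.4 points too high

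**Effect on the test.** The documents give no withdrawal rate by arm, so the rates below are assumptions. Setting: 76 randomised per arm, true success 49% in both arms, s = 0, uncorrected chi-square at two-sided 0.05, by simulation.

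| Withdrawn, inflated v sham | Observed rates | Type I error, withdrawn left out | Type I error, all kept |
|---|---|---|---|
| 5% v 2% | 51.6% v 50.0% | 5.6% | 4.5% |
| 5% v 0% | 51.6% v 49.0% | 6.2% | 4.5% |
| 10% v 5% | 54.4% v 51.6% | 6.4% | 4.5% |
| 10% v 2% | 54.4% v 50.0% | 8.4% | 4.5% |
| 10% v 10% | 54.4% v 54.4% | 5.1% | 4.5% |

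Fisher's test, also named in the plan, gives about 5% at 5% v 2% and a little over 7% at 10% v 2%.

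**Sensitivity to s.** At 10% v 0% with s = 0 the error is about 10%. If a quarter of the withdrawn women would have counted as successes, the inflated arm reads (0.49 − 0.10 × 0.25) / 0.90 = 51.7% and the error is 6.3%. If 49% would have, the rate is (0.49 − 0.10 × 0.49) / 0.90 = 49.0% and there is no bias.

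**When there is a real effect.** With true rates of 60% v 49% and 10% v 2% withdrawn as failures, the observed rates are 0.60 / 0.90 = 66.7% and 0.49 / 0.98 = 50.0%. A difference of 11 points then reads as about 17.

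**The case against.** The strongest reply is that the plan is silent on this point rather than wrong. Five stronger readings are tempting, and the documents do not support them.

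- **That the protocol excludes these women from the primary analysis.** It does not say so. Where it means exclusion it uses the words: of a woman who delivers outside the system, "she will be withdrawn from the study analysis". The patient-request rule has no such phrase. The question about delivery data concerns future collection, and nothing says ECV data already recorded are discarded.
- **That the 10% allowance proves it.** No cause is given for the allowance. Failed placement or inflation and outside delivery are separate withdrawal routes and could account for it.
- **That only failures are removed.** A woman who stops before any attempt has no ECV result. One who stops between attempts might have been turned later, and an off-protocol ECV may succeed. These women are unconverted when they stop; they are failures only under a definition that the plan lacks.
- **That the inflated arm has more pain.** Potential Risks calls this unlikely but possible. Both arms have the device inserted, and women are blinded.
- **That declining another attempt is withdrawal.** Four attempts is a maximum, so a woman who ends after two can be recorded as unsuccessful within the protocol.

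The plan also commits to publishing the withdrawal percentage and reasons. All of this stands and limits the claim. It does not supply a rule. A woman who does withdraw mid-procedure still has no stated arm, denominator or outcome, and the promised reporting is not by arm.

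**Conclusion.** The point holds in conditional form. The gap is certain: no section keeps a woman who withdraws before or during the procedure in her randomised arm or says how her primary outcome counts. Her exclusion is the likely reading, given the denominator of women who undergo ECV, the dropout allowance for an outcome read at the same visit, and the lack of an all-randomised analysis set. It is an inference all the same.

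If she is excluded, success rates are overstated, by 5.4 points at 10% withdrawal when all those withdrawn count as not converted. Bias towards the device needs a further condition, that stopping is commoner in the inflated arm. Under moderate assumptions the effect is small (type I error 5.6% at 5% v 2%). It becomes material at 10% v 2% (8.4%), a scenario in which withdrawals on request alone take up the inflated arm's whole 10% allowance. With equal withdrawal the test is not distorted. This should be fixed, because the remedy is cheap and unrecorded outcomes may be lost for good. It does not show that the trial's comparison is invalid.

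**What to change.** Amend the withdrawal section and the Statistical Analysis Plan as follows.

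1. Distinguish stopping the device or the attempts from withdrawing permission to use data.
2. Define the primary analysis set as all randomised women in their assigned arm.
3. For a woman who stops, complete item 29 from the ultrasound that Visit 1 already places at device removal. A fetus not cephalic at that point is recorded as N, including when she stops after inflation but before any attempt. State in advance what is done if no scan is obtained.
4. Record the result of any off-protocol ECV as a separate item, used only in a sensitivity analysis of final presentation.
5. If she withdraws data permission, stop collection and use what was obtained up to then as far as her consent allows.
6. Report stops by arm and by attempt number, with reasons.

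The cost is amendment wording and one extra data item, with no added visit. Observed success rates will be slightly lower, because stopping counts as not converted. The change concerns data handling and analysis only and leaves clinical management as it is.
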